### C3. Participants:

Daily cigarette smokers (n=200) will be recruited from the local community using standard media outlets. We will also submit a Research Data Request to obtain a recruitment report of MUSC patients who potentially meet eligibility criteria. The study team will not cold-contact any patients who have opted out of receiving contact about research or who have met the maximum number of contact attempts at the time of recruitment. We will reach out to these potential participants via MyChart message, text message, phone call, or email no more than three times via any one contact method. Although we anticipate having 180 participants complete the study, here we have increased this sample size to 200 in anticipation of attrition. We will recruit an equal number of young adult (21-30) and older adult smokers (>30) to allow for exploratory analysis on the impact of age. In/exclusion criteria are designed to enroll relatively healthy smokers who predominately use cigarettes and have limited experience with e-cigarettes. Inclusion criteria include a) adults who have been smoking at least five cigarettes daily for the past year (baseline CO > 8ppm), b) rate their interest in using e-cigarettes as >5 on a 0-10 scale, c) have a smartphone that can receive text messages and has access to the internet or has an e-mail account they check daily and d) must be age 21 or older. Exclusion criteria include a) use of tobacco products other than cigarettes, including e-cigarettes, on ten or more days in the past 30 days, b) current use of cessation medications, c) pregnant, trying to become pregnant, or breastfeeding, d) recent history of cardiovascular distress in the last three months (e.g., arrhythmia, heart attack, stroke, uncontrolled hypertension), e) history of a seizure disorder, f) household member currently enrolled in the study.

#### **C4. E-cigarettes and E-liquids:**

E-cigarette device will be chosen based on the following guiding principles: 1) can deliver power in the desired range (20W, 40W), 2) can be fixed at those settings by experimenters, but not easily altered by participants, and 3) is able to provide objective measurement of e-cigarette use. We are aware of at least one device that meets these criteria: Evolv DNA 75c Color with Tobacco Mini Tank. We will utilize eScribe software, available specifically for researchers for the Evolv device, which allows experimenters to fix the device settings such that they cannot be altered by participants, and can blind the participants to the power settings. This software can also retrieve information about the participant's use of the product including the number of puffs, the puff duration, and the puff volume, which we view as a great strength. If this device becomes unavailable, we will choose another e-cigarette device using the same principles, and expect that the proliferation of devices will add to our list of options from which to choose.

Nicotine concentrations will be 3 vs. 12 mg/ml, chosen based on preliminary data from [name] (co-mentor) trials showing these are the most popular concentrations for devices with wattages in the range used here. The high nicotine concentration is in a range that has been shown to deliver cigarette-levels of nicotine in naïve users assigned to a low-powered device (12-36 mg/ml), and similar concentrations are currently being used in other e-cigarette clinical trials. However, the low concentration is in the range shown to be popular with higher-powered devices (3-6 mg/ml). The e-cigarette device and atomizer will be constant for all participants, but will be fixed at a low (20 W) or a high (40 W) power using the eScribe software described above. The lower power setting was chosen to be in a similar range to popular low-power, second-generation devices. The high-power setting was chosen to be in a range of available settings for popular third-generation devices and based on preliminary data from [name] lab showing it delivers cigarette-levels of nicotine at 3 mg/ml concentration with a typical e-cigarette puff duration (3.4 s, 0.1 mg nicotine / puff, unpublished data).

We recognize that multiple device characteristics contribute to changes in power including battery voltage, coil resistance, and coil size. The device chosen here manipulates power via changes in the voltage of the battery, holding other features constant. This design has strong internal validity because only one aspect of the device is changing. Although voltage is being manipulated here, we view the results as having implications for all of the determinants of power described above.

E-liquid will be purchased from American E-liquid, which has been used in other research studies and is available in a wide range of concentrations and flavors. E-liquid flavors will be chosen based on the three most popular flavors at the time of study onset.

#### **C5. Procedures:**

**C5a. Screening, Baseline, and Randomization (Visit 1):** Potential participants will be phone screened for initial eligibility. Alternatively, participants may complete a Redcap survey to determine initial eligibility. Participants will see a script that briefly explains the study. Those meeting criteria will either by consented electronically or consented at an in-person visit. Consented participants will attend an in-person visit where they complete additional baseline measures and provide a urine sample for cotinine analysis. We will provide transportation via a taxi cab company for participants who are eligible, but do not have reliable transportation to in-person visits. All participants will receive an e-cigarette and e-liquid, varying in 2x2 manner on both nicotine concentration (3 vs. 12 mg/ml) and power (20W vs 40W) (n=45cell). Participants will be given instructions

about how to fill and operate their device, similar to what might be conveyed online or in a vape shop. Participants will be told to use the e-cigarette as much as they would like, and that they are not required to use the e-cigarette or to smoke cigarettes, but we request that they do not use any non-study e-cigarettes during this time period (to avoid use of products with different characteristics than those assigned). We are forced to rely on self-report of non-study e-cigarette use, but we do not expect it to be a pervasive problem given that current e-cigarette users are excluded, and because we provide product for free. Both participants and research staff will be blind to assigned nicotine concentration and power settings. At each visit, participants will be provided with a one-week supply of e-liquid such that they could exclusively use the e-cigarette if they choose to do so. Participants will also complete a lab-based preference assessment (described below).

**C5b. Sampling (Visits 2-4):** We considered a longer sampling period but our experience in prior sampling studies is that 3 weeks is sufficient to acclimate (77). Over the three-week sampling period, participants will complete daily electronic diaries cataloging their cigarette and e-cigarette use. Each morning, participants will receive an e-mail or text message link to complete their diary. The diary will assess tobacco use the previous day including cigarette smoking, number of e-cigarette puffs per day, quit attempts, and craving. This electronic daily diary is currently being used in [name] R01 and [name] pilot study, with compliance > 90%. Participants will attend weekly in-person visits where they will complete assessments regarding tobacco use, craving, dependence, product perceptions, as well as provide expired carbon monoxide samples. Urine samples for cotinine analysis will be provided at randomization and at the end of sampling. Research staff will conduct routine device maintenance at these visits. At the end of the sampling period (Visit 4), participants will return their e-cigarette device and e-liquid, and complete the preference assessment again.

**C5d. Follow-up (Visit 5):** Participants will return to the lab one month following the end of the study to assess their cigarette smoking, e-cigarette use, e-cigarette purchases, and provide expired breath carbon monoxide.

**C5e. Modified Procedures to be Implemented During COVID-19 Restrictions:** After passing initial screening, all participants will be consented into the study through our established remote procedures, instead of having the option to complete the consent process in person. All in-person screening questionnaires that can be administered over the phone prior to the visit will be completed over the phone (demographics questionnaire, physiological & medical history, & tobacco use history). Participants who are ineligible based on these questionnaires will be paid for the visit, but not required to come in to the lab to complete the remaining screening assessments. If the participant is still eligible after completing these questionnaires, we will then schedule them to come into the laboratory to complete the remainder of the visit. For visits 2-5, we will complete any questionnaires remotely that we can complete remotely. For interview-administered questionnaires, we will call participants in advance of the visit and complete the questionnaire over the phone via interview with study staff. For questionnaires that are completed independently by the participant, we will send them a RedCAP link prior to the visit and request that they complete the questionnaires on their own. If participants fail to complete these questionnaires on their own or we are unable to reach them to complete the questionnaires, we will ask the participant to complete them at the visit in the lab.

Participants will be called 24 hours prior to all visits to confirm they are not experiencing any symptoms of COVID-19. All participants for each visit will be required to wear a mask and remain six feet away from the research staff and others when possible. When staff and participants must interact (for CO collection and e-cigarette dispersal), at least six feet of distance will be maintained by placing materials on a desk/table six feet away from the participant and then staff stepping away while the participant approaches to retrieve materials. All surfaces will be sanitized prior to the visit and after the visit.

## C6. Compensation:

Participants will receive \$25 for Visits 1 and 4 (1.5 hours), \$15 for Visits 2, 3, and 5 (45 minutes), and a \$75 completion bonus if they complete all visits. Participants can earn additional payment for daily diaries based on # completed (up to \$25/week). Participants who attend all sessions and complete all diary entries could earn \$245.

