### ***Concurrent Use of E-cigarettes & Smoking***

Per above, the most common effects from too much nicotine are nausea, headache, and disturbed sleep. The sampling period is three weeks in duration, and thus we do not expect sustained patterns of dual use. We will track adverse events at every study contact, and will have a toll-free number available for participants to call if they experience an adverse event (AE). All study contacts will remind participants of this number. Participants will be encouraged to contact study staff as soon as possible for serious events. If they wish, they may contact their local MD or give the study medical advisor permission to do so. We will withdraw participants who have a serious AE, become pregnant or begin breast-feeding. For other AEs, if the study medical advisor ([name]), the participant's physician or the participant wishes it, the participant will be withdrawn from the study.

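### The completion bonus in C6 has no exception for participants the study withdraws, so disclosing an event that leads to withdrawal, pregnancy above all, costs $75

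*Combined protocol and SAP*

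**What the plan says.** Section C6 sets out three kinds of payment. Each visit is paid separately: $25 for Visits 1 and 4, and $15 for Visits 2, 3 and 5. Diaries are paid pro rata, up to $25 a week: "Participants can earn additional payment for daily diaries based on # completed". On top comes a $75 "completion bonus if they complete all visits". The section mentions no part payment, no make-up visit and no exception for a participant who leaves because the study requires it.

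The withdrawal rule is in section 2.2, under Concurrent Use of E-cigarettes & Smoking: "We will withdraw participants who have a serious AE, become pregnant or begin breast-feeding". For any other AE, the participant is withdrawn if the medical advisor, the participant's physician or the participant wants it. The same section says that AEs are asked about at every contact and that participants can telephone to report one.

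On pregnancy, section 2.2 (Use of E-cigarettes) provides for a check when the study starts. Sections 1.2 and 2.1 place the urine test at screening. No later test is described there or in Table 1.

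**The concern.** The two sections were written for different purposes and work against each other. Section 2.2 relies on participants telling staff about events so that the study can act. C6, read literally, takes away the largest single payment from a participant whose disclosure leads to withdrawal.

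What is at stake is a safeguard. Pregnancy shows it best, because withdrawal is automatic and, after the screening test, the plan describes no means of detection other than the participant's own report. A participant who stays silent can complete all visits and be paid the bonus. One who speaks up cannot.

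**Working it through.** **Inputs.** All payments are from C6: $25 for each of Visits 1 and 4; $15 for each of Visits 2, 3 and 5; bonus $75; diaries up to $25 a week. The number of diary weeks is three, from C5b: "Over the three-week sampling period, participants will complete daily electronic diaries".

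**The plan's own total.** Visits: 2 × $25 + 3 × $15 = $95. Diaries: 3 × $25 = $75. Sum: $95 + $75 + $75 = $245. This reproduces the figure in C6 ("Participants who attend all sessions and complete all diary entries could earn" $245).

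**Weight of the bonus.**
- Share of the maximum: 75 / 245 = 31%.
- Share of money that depends on visits: 75 / (95 + 75) = 75 / 170 = 44%.

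**What withdrawal costs.** Assume full diary completion to date and payment for the visit at which withdrawal happens. C6 does not spell this out.
- At Visit 2: received 25 + 15 + 25 = $65; forgone 245 − 65 = $180.
- At Visit 3: received 25 + 15 + 15 + 50 = $105; forgone 245 − 105 = $140.
- At Visit 4: received 25 + 15 + 15 + 25 + 75 = $155; forgone 245 − 155 = $90.

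In each case only $75 of the forgone sum is the bonus. The rest ($105, $65 and $15) is pay for visits and diaries not yet done, which any withdrawal would end. The penalty that C6 itself creates is therefore $75, whatever the time of withdrawal. Because Visit 5 counts as a visit, a participant withdrawn as late as Visit 4 still loses all of it.

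**Which disclosures are affected.**
- Serious AE, pregnancy or breast-feeding: withdrawal is automatic, so the bonus is lost.
- Other AE: the bonus is lost only if the medical advisor, physician or participant opts for withdrawal.
- AE handled without withdrawal: nothing is lost.

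**The same rule applied to a missed early visit.** Missing Visit 2 or 3 costs 15 + 75 = $90. The visit-dependent money left for Visits 4 and 5 then falls from 25 + 15 + 75 = $115 to $40.

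**The case against.** The strongest reply is that C6 never says a withdrawn participant forfeits the bonus. That is inferred from the stated condition and from silence, and the consent form may settle it. This stands as a limit: the consent form was not available, and if it already contains an exception, C6 merely needs to say the same.

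It is also fair that most AE reports cost nothing. Section 2.2 expects the most likely AE to be rare (about 5%) and mild, handled by advice, and section 1.2 reports no serious AEs in the team's current e-cigarette studies. The penalty therefore attaches to events that end in withdrawal, not to AE reporting in general. The documents give no evidence on how participants would respond to it.

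Three stronger readings are tempting, and the documents do not support them.
- A reader might infer that concealment would bias a safety comparison between arms. Neither the Specific Aims, C8 nor the Statistical Analysis Plan contains such a comparison. The remark in A2 that high concentration with high power may be aversive is an argument about reinforcement, not a forecast of AEs.
- A reader might infer that losing the bonus puts the primary outcome at risk. Under C7c, daily cigarette counts come from the electronic diary, which is completed remotely and paid independently of visits. C8 and the Statistical Analysis Plan place outcomes at Visit 4 in an ambiguous phrase, but the stated source of cigarettes per day is the diary. A missed Visit 4 or 5 exposes the preference and purchase tasks, carbon monoxide, cotinine, week-3 device data and follow-up.
- A reader might conclude that the bonus should depend on Visits 4 and 5 alone. That would weaken the incentive for Visits 2 and 3, where AEs are assessed and where carbon monoxide and device data are collected for the weekly analysis. It is an optional trade-off, not a correction.

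**Conclusion.** The point holds in narrow form. As C6 and section 2.2 stand, a participant who discloses an event that leads to withdrawal before Visit 5 cannot meet the bonus condition and loses $75: 31% of the maximum payment and 44% of visit-dependent pay. The case is clearest for pregnancy, where withdrawal is automatic and detection after screening depends mainly on disclosure.

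The arithmetic is exact. The conclusion rests on reading C6 literally and on there being no exception in the consent form. The effect on disclosure is inferred from the incentive, and its size is unknown. Nor do the documents give any basis for how many participants would be withdrawn this way. This is a cheap improvement to a safeguard; it does not threaten the trial's main comparison.

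**What to change.** Add one sentence to C6: a participant withdrawn under section 2.2 for an adverse event, pregnancy or breast-feeding keeps the $75 completion bonus. Say the same in the consent form if it does not already do so, so that participants know it before any event occurs. The sentence should also make clear whether it covers withdrawal at the participant's own wish after a non-serious AE, since section 2.2 lists that route beside the medical advisor's and the physician's. The withdrawal criteria themselves are untouched.

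The cost is $75 per participant withdrawn. As a bound rather than an estimate, C8 allows for 180 − 4 × 40 = 20 losses from all causes. If every one were of this kind, the cost would be 20 × $75 = $1,500. The small downside is a possible incentive to report an event in order to leave early with the bonus. It is limited because pay for the remaining visits and diaries would still be lost.

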## C7. Measures

Table 1. Study Measures	V1 (SCR/BSL)	V2	V3	V4	V5 (FU)
Screening Assessments					
Demographics, Medical, Tobacco, Drug, & Alcohol Hx	X				
Measures of relative reinforcement and dependence					
Purchase Tasks	X			X	X
Preference Assessment	X			X	

Dependence (FTND/WISDM/Penn State)	X		X	X
Measures of smoking behavior				
Daily Diaries	Start	-----	-----	End
Detailed measures of e-cig use collected from device	Start	-----	-----	End
Timeline follow back		X	X	X
Follow-up tobacco use questionnaire				X
Measures of nicotine delivery and sensorimotor cues				
Urinary cotinine (Nicotine Exposure)	X	X		X
Withdrawal / Craving (MNWS/QSU)	X	X		X
Sensorimotor items added to mCEQ	X	X	X	X
Other self-report questionnaires				
Product Satisfaction (mCEQ)	X	X		X
Perceived Health Risks	X	X		X
Adverse Event Assessment		X	X	X
Physiological Assessments				
Carbon Monoxide (Smoke Exposure)	X	X	X	X

**C7a. Screening Assessments:** Preliminary eligibility will be determined on the phone before participants are either consented electronically or invited for an in-person visit to provide consent. Alternatively, participants may complete a Redcap survey to determine initial eligibility. Participants will see a script that briefly explains the study. Consented participants will attend an in-person visit where they complete screening questionnaires related to demographics, tobacco use history, and expired carbon monoxide. During the COVID-19 restrictions, all consenting will be done remotely.

**C7b. Measures of Relative Reinforcement and Dependence:** Relative reinforcement will primarily be assessed using a lab-based preference assessment, a well-validated measure of reinforcement value. First, participants will sample their usual brand cigarette to standardize time since last cigarette. Then participants will sample their assigned e-cigarette and e-liquid. Immediately after sampling each product, participants will complete questionnaires about that product, including a modified version of the mCEQ, a perceived health risk measure, and a purchase task. Then, participants will complete the preference assessment in which over a period of 30-minutes and 10 trials (three-minute inter-trial interval), participants choose between taking two puffs of the e-cigarette, two puffs of their usual (own) brand cigarette, or abstaining from both. This task measures the impact of concentration and power on changes in the relatively reinforcement value of smoking compared to using the e-cigarette. The primary outcome is the number of choices to smoke the usual brand cigarette, but secondary outcomes include the number of choices to use the e-cigarette and to abstain. We considered utilizing a cigarette other than the participant's usual brand to control for novelty, but changes in relative reinforcement value of the participants' usual brand cigarette are most relevant from a public health perspective. Our lab space includes ventilated smoking rooms equipped with cameras and intercom, which allow us to guide participants through the task from a separate area. A secondary measure of reinforcement value will be the purchase tasks—hypothetical tasks in which participants estimate the intensity with which they would use cigarettes and e-cigarettes at a variety of prices. An individual's sensitivity to the cost of a tobacco product is considered to be an estimate of that product's reinforcement value. Dependence will be assessed at in-person visits using established measures of cigarette and e-cigarette dependence (Fagerstrom Test for Nicotine Dependence, Wisconsin Inventory of Smoking Dependence Motives, Penn State E-cigarette/Cigarette Dependence Scale). [name] is utilizing both the preference task and the demand measures in her ongoing pilot trial focused on PG/VG ratio in e-liquids.

**C7c. Measures of tobacco use:** Daily cigarette use will be captured using an electronic daily diary in which participants report the number of cigarettes they smoked (< 2 min/day). We will collect expired breath carbon monoxide at each weekly visit, which provides an objective measure of recent exposure to smoke, but is unaffected by e-cigarette aerosol. During weekly assessments, we will retrieve information about e-cigarette use from the device, using eScribe software described above. The software provides the number of puffs taken each day and the average puff duration. Within weekly lab visits, participants will retrospectively report these outcomes via timeline followback.

**C7d. Measures of Nicotine Delivery:** Participants will provide urine samples for testing of cotinine (primary metabolite of nicotine) within our Departmental lab. We will not be able to discriminate the source of nicotine

(cigarette vs. e-cigarette), but will be able to test whether overall nicotine exposure has increased or decreased from baseline. We will also measure the quantity of nicotine liquid that participants use by weighing the e-liquid bottles at distribution and at each visit, which combined with the concentration provides some information about nicotine intake from the assigned e-cigarette. We will also assess subjective assessments of nicotine effects including withdrawal (MNWS), and craving to smoke (QSU).

**C7e. Measures of Sensorimotor Cues:** Because e-cigarettes are relatively new products, there are no validated measures to assess reinforcement from sensorimotor cues. In consultation with [name] (co-mentor) we will include items that assess participant satisfaction with throat hit, aerosol volume, aerosol temperature, and flavor. These items will be added to a modified version of the mCEQ, which will assess reward and satisfaction from both cigarettes and e-cigarettes.

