## A. Significance

### A1. The Rise of E-cigarettes and their Impact on Public Health:

E-cigarettes are now used by 5.5% of adults, and 8.9% of young adults. The most common reason for trying e-cigarettes among adults is to reduce or quit cigarette smoking. The level of toxicant exposure from e-cigarettes is still not entirely understood, but most public health experts agree that e-cigarettes deliver fewer toxicants than combustible cigarettes. Thus, for smokers who try e-cigarettes, the health impact of use is dependent on whether they reduce or discontinue using cigarettes. For some users, e-cigarettes may facilitate a reduction or cessation in cigarette smoking. However, most smokers who try e-cigarettes either abandon them completely after a short period or, more predominantly, engage in dual use. We recognize the polarizing debate over e-cigarettes, with some emphasizing potential dangers, and others emphasizing potential benefits. We do not take a stance either way. Rather we argue that the impact (either benefits or harms) of e-cigarettes is strongly dependent on their uptake and ability to curb cigarette use. It is therefore important to understand the factors that lead to these different use patterns.

One obvious influence on e-cigarette adoption is the wide variability of both devices and e-liquids on the market. All e-cigarettes contain a lithium battery, a reservoir that contains e-liquid, and an atomizer that heats the e-liquid to create an aerosol that is delivered to the user. Beyond this basic structure, e-cigarettes vary on a wide range of dimensions including: concentration of nicotine in the e-liquid, flavoring, appearance, power, and ability for customization. For current smokers who try e-cigarettes, these product characteristics affect their uptake by influencing the relative reinforcement value of e-cigarettes in comparison to cigarettes. Reinforcement value is well established as one of the primary determinants of tobacco use.

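### Weighing only the e-liquid bottles miscounts liquid held in or discarded from the tank, and for equal residue the nicotine error in mg is four times larger at 12 than at 3 mg/ml

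*Combined protocol and SAP*

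**What the plan says.** C7d, on nicotine delivery, describes the measure in one sentence. It opens "We will also measure the quantity of nicotine liquid that participants use", and gives the method and its purpose together: "by weighing the e-liquid bottles at distribution and at each visit, which combined with the concentration provides some information about nicotine intake", meaning intake from the assigned product. No formula follows.

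Other sections bear on it:

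- C4 names a tank device, the "Evolv DNA 75c Color with Tobacco Mini Tank", and sets the two strengths: "Nicotine concentrations will be 3 vs. 12 mg/ml". Tank capacity is not given.
- C5a says participants are taught to fill the device themselves and receive a week's supply of liquid at a time.
- Section 1.2 (Study Procedures) places the first lab use of the assigned e-cigarette within Visit 1, with the take-home supply handed over at the end of that visit.
- C5b says "Research staff will conduct routine device maintenance at these visits", without saying what happens to liquid in the tank. Device and e-liquid come back at Visit 4.

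No section says that the tank or device is weighed, emptied back into the bottle, or subtracted.

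**The concern.** A bottle loses weight when liquid is poured into the tank, not when it is vaporised. Bottle loss equals use only if the tank holds the same amount at the start and end of the interval and nothing is discarded. The plan does not secure either condition.

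The discrepancy is then multiplied by the assigned concentration, so its size in mg depends on a randomised factor. C7d itself accepts that cotinine cannot tell cigarette nicotine from e-cigarette nicotine, and the device log gives puffs rather than nicotine. Bottle weight times concentration is therefore the only described estimate of nicotine taken from the study product.

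The relative error is greatest where little liquid is used. A1 says that "most smokers who try e-cigarettes either abandon them completely after a short period or, more predominantly, engage in dual use", so light use is a realistic pattern. A2 also raises the rival hypothesis that users given a weaker liquid or lower power make up for it by consuming more. A measure that leans towards a concentration difference when that rival is true would mislead on a question the protocol itself poses.

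**Working it through.** The plan states no figure for this measure, so there is nothing to reproduce. The check is a mass balance.

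**Inputs from the documents:** concentrations C of 3 and 12 mg/ml (C4); bottles only, weighed at distribution and each visit (C7d); a tank filled by participants (C4, C5a); more liquid consumed at lower power or concentration (A2).

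**Assumed, because the documents are silent:** volume vaporised V, tank residue at the start and end of an interval, and volume discarded D.

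**1. The error.**
- Bottle loss = V + (end residue − start residue) + D
- Let r = end residue − start residue + D, the net residue.
- Apparent nicotine = C × (V + r); nicotine in the liquid vaporised = C × V; error = C × r.

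**2. By arm, for equal r.** The ratio of errors is 12/3 = 4. The false between-arm difference is (12 − 3) × r = 9r.

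| Assumed r (ml) | Error at 3 mg/ml (mg) | Error at 12 mg/ml (mg) | False difference (mg) |
|---|---|---|---|
| 1 | 3 | 12 | 9 |
| 2 | 6 | 24 | 18 |
| 4 | 12 | 48 | 36 |

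**3. Effect on the arm ratio.** The relative error is r/V.
- Equal use, V = 5 ml and r = 2 ml in both arms: apparent 12 × 7 = 84 mg and 3 × 7 = 21 mg. The ratio is 4, the same as the true 60/15. The mg difference is 63 against a true 45, but the ratio is unbiased.
- Full compensation, V = 5 ml at 12 mg/ml and 20 ml at 3 mg/ml: the true value is 60 mg in both arms. With r = 2 ml the apparent values are 12 × 7 = 84 mg and 3 × 22 = 66 mg. That is a false 18 mg difference (18/60 = 30%) and a ratio of 84/66 = 1.27 where the truth is 1. A log transformation would not remove it.

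**4. Light against heavy use.** With r = 2 ml, the relative error is 2/2 = 100% at V = 2 ml and 2/20 = 10% at V = 20 ml.

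**5. Carried over or emptied.** Take V = 5 ml a week, 2 ml in the tank at each visit, and an empty tank at the start.
- Tank carried over: weekly bottle loss is 7, 5, 5 ml. The total is 17 against a true 15, so the error is 2 ml (the last residue).
- Tank emptied and discarded at each visit: weekly loss is 7, 7, 7 ml. The total is 21 against 15, so the error is 6 ml.

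**6. A negative error is possible.** Suppose the device goes home holding 2 ml from the Visit 1 lab session, and the participant vaporises 1 ml and never refills. Bottle loss is 0 against a true 1 ml. Then r = 1 − 2 = −1 ml, and intake is understated by 3 mg at 3 mg/ml or 12 mg at 12 mg/ml.

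**The case against.** The best defence is that C7d claims little. It offers partial information, sets no formula, and nowhere equates bottle loss with intake. The measure has no row in Table 1 and is not named in C8 or the SAP, where the hypotheses rest on cigarettes per day, puffs per day and preference or demand. The device logs puffs objectively, so light users and abandoners can be identified without the bottle weights. All of this stands, and it keeps the point minor.

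The defence is also right about size and direction. Tank volume and weekly consumption are not in the documents. Residue carried forward largely cancels. If the tank is already filled from the lab session, the error may be near zero or negative.

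A reader might go further in three ways that the documents do not support:

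- **That the false difference between arms is fourfold.** The factor of four applies to the error within each arm. The between-arm difference is 9 mg per ml of net residue, and the arm ratio is unbiased when residue is the same fraction of use in both arms.
- **That all unused product is miscounted.** Liquid left in the bottle is correctly excluded. Only liquid in, or lost from, the tank is at issue.
- **That grams will be read as millilitres.** The plan does not say so. The conversion step is simply not written down, and if the liquid base is the same across arms, leaving it out would not change the arm ratio.

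None of this removes the miscount. Followed as written, the method still assigns tank liquid wrongly, and A2 gives reason to doubt that residue would be the same fraction of use in both arms.

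**Conclusion.** The point holds as a minor measurement defect. For an assumed net residue of 1–4 ml, equal in the two arms, the false between-arm difference is 9–36 mg. Under full compensation with the assumed volumes above, equal true intakes of 60 mg would read 84 and 66 mg. These are illustrations. The documents fix the factor of four and the 9 mg per ml, but not the residue, the direction of the error, or whether it accumulates.

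It would be wrong to infer that a hypothesis test or the trial's main conclusion is at risk. The primary analysis, Hypotheses 1–3 and the sample size do not use this measure. The reason to act is that it is the only described e-cigarette-specific estimate of nicotine intake, and that weights not taken at a visit cannot be recovered later.

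**What to change.** In C7d, state that the tank or device is weighed together with the bottles:

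- at distribution, after the Visit 1 lab use;
- at each later visit, before and after maintenance;
- at the Visit 4 return.

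Compute liquid used in each interval as the combined weight when the participant leaves one visit, including newly issued bottles, minus the combined weight on arrival at the next, before maintenance. Staff discards and part changes then fall outside every interval. Convert weight to volume, using the density of the supplied liquid, before applying mg/ml. Check any interval with no puffs in the device log against the weight change.

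Liquid spilled or thrown away at home would still count as used, and the puff log is the only check on that.

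The cost is a few extra weighings per visit, at visits already held and with weighing already planned. No change is needed to the sample size or to the hypothesis tests.
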